5.4 Adverse Events

Adverse events (AEs) will be summarized for main reporting efforts. Adverse events are defined as any untoward medical occurrences in a Subject whether device-related or not. All AEs will be recorded on the appropriate CRF and documented in the Subject's permanent medical record. The Investigator at each Site is ultimately responsible for reporting all AEs to the Sponsor, as well as to the IRB, as applicable.

Adverse events will be summarized by incidence (i.e. a specific AE will not be counted more than once for a Subject within each window) in each analysis time window for each Subject. The denominator for each window will be calculated as the number of enrolled Subjects remaining in follow-up as of the beginning of the analysis window (Subjects must have an initial procedure date). At a minimum, separate summaries by AE relationship and severity will be prepared.

Partial dates (month and/or day unknown) for AE onset and AE resolution dates will be allowed for analysis. Exact imputation logic will be documented in the appropriate specifications document. In general, partial dates will be imputed to be most conservative with regards to timing after initial procedure date.

Selected AEs will be reviewed by the independent CEC and adjudicated with regard to device and/or procedure relationship and severity. Specific AEs of clinical interest in this Subject population will include, but are not limited to: death-related AEs, stroke, paraplegia/paraparesis, and MACCEs. Reported AEs which potentially meet the definition of AEs of clinical interest will be referred to the CEC for review and adjudication to the study Protocol's definitions provided for these events. The adjudicated opinion of the CEC will also be used in analysis and reporting of adverse event data.

5.4.1 Adverse Event Relationship

Each reported AE will be assessed by the Investigator for its primary suspected relationship to the device or procedure. If the Site-reported primary relationship of the AE is any of the following it will be considered a (Site-reported) device and/or procedure related AE: related to device, related to procedure, or related to device and procedure.

Relationships include:

Related to device

The functioning or characteristics of the device caused or contributed to the AE.

Related to device and procedure

The device AND the endovascular procedure caused or significantly contributed to the AE.

Related to procedure

The endovascular procedure (and not the device) caused or significantly contributed to the AE.

Related to other procedure

Other procedure performed caused or significantly contributed to the AE.

Related to disease

Original (treated) disease caused or significantly contributed to the AE.

Not-related

An AE which cannot be attributed to the device or procedure.

Unknown relationship

The relationship of the AE to the device or procedure cannot be determined.

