4.6 Imaging

5.0 Statistical Analyses

5.1 Analysis Populations

All enrolled Subjects with an attempted initial procedure (have non-missing initial procedure date) will be included in analysis as follows:

- Primary Endpoint: all Subjects will be included; Subjects without known mortality status through 30-days will be considered failures for this (i.e. assumed dead for the primary endpoint analysis).
- Secondary Endpoint of technical success: all Subjects will be included; any Subject missing evaluation on this will be counted as a failure for this endpoint.
- Secondary Endpoint (MACCE, MACCE components, and aorta-related mortality): all Subjects will be included.
- Secondary Endpoints (device migration, endoleak): Subjects with known status (have had imaging done or endpoint event reported) at each follow-up window will be included; an endpoint event (endpoint failure) will be reported from a Site-reported adverse event. Subjects without imaging reported in a window but with an adverse event meeting the endpoint definition in a window will count as having an endpoint event for that window. Subjects without imaging reported in a window and with no endpoint event reported in window will not count towards the denominator for that window.

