5.2 Timing of Analyses

Analysis of the study results will be ongoing throughout enrollment. Regular case review by the Data and Safety Monitoring Board (DSMB) and Sponsor will occur throughout enrollment.

DSMB data review will be instituted as follows:

- For the first four (4) Subjects, procedural reports will be provided to FDA and the DSMB Chairman within 5 working days of endovascular treatment and will include available procedural narratives, reports and any preliminary Adverse Events (AEs.
- Reporting Subject and device performance data to the DSMB following the endovascular treatment of every two (2) Subjects through patient 20 and every five (5) patients for patient 20-30, including the available 1 month follow-up visit data for preceding cohorts.

- Reports will include information on Subject baseline characteristics, deaths, and a summary of all serious adverse events such as paraplegia, paraparesis, stroke, and aortic rupture.
- Reports will also include observed device and/or procedure related adverse events such as deployment anomalies, branch lumen obstruction or occlusion, adverse events that result in secondary interventions for additional device implantation, and adverse events that result in conversion to open surgical repair.
- Reports provided to the DSMB will be submitted to the FDA as IDE supplements and a summary will be sent to each participating Site IRB.

The primary analysis will occur when enrollment is complete, and all available enrolled Subjects have completed the 1 month follow up assessment. A final DSMB review will be conducted when all enrolled Subjects have reached the 1 year follow-up window. Serial analyses of long-term results will occur during the follow-up period. No adjustments to the overall alpha level will be made since this is an exploratory study designed to evaluate basic feasibility.

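### The related-AE composite in SAP 5.4.1 leaves out events of unknown relationship, so its incidence is a lower bound and should be shown with and without them (minor)

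*Combined protocol and SAP*

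**What the plan says.** SAP 5.4.1 makes the investigator the assessor: "Each reported AE will be assessed by the Investigator for its primary suspected relationship to the device or procedure". Of the seven categories, three make an event count as related: "it will be considered a (Site-reported) device and/or procedure related AE: related to device, related to procedure, or related to device and procedure". The other four are related to another procedure, related to disease, not related, and unknown relationship. The last is defined as "The relationship of the AE to the device or procedure cannot be determined".

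Three other places bear on how the composite is used:

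- SAP 5.4 on reporting: "At a minimum, separate summaries by AE relationship and severity will be prepared". AE incidence is counted once per subject per window, over the enrolled subjects still in follow-up when the window opens.
- SAP 5.4 on adjudication: "Selected AEs will be reviewed by the independent CEC and adjudicated with regard to device and/or procedure relationship and severity". The CEC's opinion is also to be used in analysis and reporting. The visible text does not say whether it or the Site's assessment prevails.
- SAP 5.2 on DSMB reports: "Reports will also include observed device and/or procedure related adverse events such as deployment anomalies". The same section also gives the DSMB baseline characteristics, deaths and a summary of all serious AEs.

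**The concern.** An investigator who cannot tell whether the device or the procedure caused an event has not ruled either out. Under 5.4.1 that event is absent from the numerator of the related-AE composite. A reader who sees one related-AE percentage may take it as the estimate, when it includes only events with a positive attribution.

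The plan treats some other unknowns differently. For the primary endpoint in SAP 5.1, "Subjects without known mortality status through 30-days will be considered failures for this", and a missing technical success evaluation also counts as a failure. For relationship, an unknown goes towards the lower event rate, and no reason is given.

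The study is a small, single-arm feasibility study reported descriptively (SAP 2.2 and 2.4). The definitions behind the percentages therefore shape what readers conclude about safety. What is at stake is the related-AE figure in the AE summaries and, if the 5.4.1 definition is applied there, in the related-AE part of the DSMB reports.

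**Working it through.** The documents state no related-AE rate and no expected share of unknown relationships, so there is no planned figure to reproduce. The check is a bound.

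**Inputs**
- n = 30 subjects (SAP 2.2; the Protocol Summary says up to 30).
- r = subjects with at least one AE in the three related categories. Assumed: 6.
- u = subjects with no such AE but at least one AE of unknown relationship. Assumed: 0 to 4.

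**Formulas**
- Composite as defined in 5.4.1: r/n.
- Composite with unknowns counted as related: (r + u)/n.
- Gap: u/n, which is never negative. At n = 30, each subject adds 1/30 = 3.3 percentage points. In later windows with fewer subjects at risk, the step is larger.

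**Results for r = 6, with exact (Clopper-Pearson) 95% intervals**

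| u | Unknowns excluded | Unknowns counted as related | Gap |
|---|---|---|---|
| 0 | 6/30 = 20.0% (7.7 to 38.6) | 6/30 = 20.0% (7.7 to 38.6) | 0 |
| 1 | 20.0% | 7/30 = 23.3% (9.9 to 42.3) | 3.3 points |
| 2 | 20.0% | 8/30 = 26.7% (12.3 to 45.9) | 6.7 points |
| 3 | 20.0% | 9/30 = 30.0% (14.7 to 49.4) | 10.0 points |
| 4 | 20.0% | 10/30 = 33.3% (17.3 to 52.8) | 13.3 points |

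If relationship in the other categories is taken as correct, the true incidence lies between the two columns. It equals the left column if no unknown event is truly related, and the right column if, in each of the u subjects, at least one is.

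**Can the upper figure be rebuilt from category summaries?** Not from counts alone, because one subject can appear in several categories. Suppose 6 subjects have a related AE and 4 have an unknown AE. The number with either is 6 if all four are among the six, and 10 if none are. The proportion could be anything from 6/30 = 20.0% to 10/30 = 33.3%, and the category counts do not show which.

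**The case against.** The case against a stronger claim is good, and most of it stands.

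- **Unknown is not recoded as not related.** A reader might infer that undetermined events are counted as unrelated. The documents do not support this: the two categories are separate, and 5.4 requires summaries by relationship. The events are outside one composite but can still be reported.
- **Bias is not established.** Exclusion gives a lower bound. Counting every unknown as related gives an upper bound, which overstates the rate if some of those events came from the disease or another procedure. Nothing in the documents says how frequent undetermined causality will be.
- **No stated endpoint depends on it.** The primary endpoint is all-cause mortality. MACCE uses death or CEC-adjudicated events, and aorta-related mortality uses a CEC question (SAP 5.3.3 and 5.3.4). Migration and endoleak use Site-reported AEs meeting the endpoint definitions (5.3.5). There is no hypothesis test (2.4).
- **The DSMB is not blind to these events.** It receives a summary of all serious AEs (5.2) and a comprehensive AE summary (6.0). A reader might infer that unknown-relationship events escape safety monitoring, but the documents do not support that.
- **There is no uniform worst-case rule to breach.** Subjects with neither imaging nor a reported event leave the migration and endoleak denominators (5.1), and MACCE follow-up is censored at last contact (5.3.3). The contrast with 30-day mortality is a difference in approach and not a contradiction.
- **Some text is not shown.** The bodies of 5.5.1, 8.1 and 8.2 are missing from the public version. A by-subject listing or a two-way table could be planned there, so its absence cannot be asserted. The heading of 5.5.1 refers to endpoint results, and this composite is not one.

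What remains is that nothing visible changes the composite itself. Category summaries cannot rebuild it, and CEC review covers selected AEs only, whereas the 5.4.1 definition is explicitly Site-reported.

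**Conclusion.** The concern holds as a minor point of reporting. The Site-reported related-AE incidence under 5.4.1 is a lower bound with respect to events of unknown relationship. The gap to the upper bound is u/30, or 3.3 points for each subject with only unknown candidates. In the illustration that is 20.0% against 23.3% to 33.3% for one to four such subjects. Both counts, 6 related and 1 to 4 unknown-only, are assumptions; with no such subjects the gap is zero.

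The reach is limited to descriptive AE summaries and, if 5.2 uses the 5.4.1 definition, the related-AE part of the DSMB reports. The documents do not support the claim that the plan's safety conclusions or any endpoint are biased in the device's favour.

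One condition applies to the bounds. Not related is defined as "An AE which cannot be attributed to the device or procedure", which lies close to the definition of unknown. If Sites place undetermined events there, the upper figure will miss them.

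**What to change.** In SAP 5.4.1, state that the subject-level incidence of device and/or procedure related AEs will be reported two ways, side by side, in the AE tables and the DSMB reports: with *Unknown relationship* counted as related, and with it excluded. Give the CEC-adjudicated relationship wherever it exists. Neither figure need be the sole headline, since together they show the range.

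A short clarification to Sites of how the not-related and unknown categories differ would protect the upper figure.

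The cost is a sentence in the SAP, one extra column, and an upper figure that may look less favourable. No additional data collection is needed, because relationship is already recorded for each reported AE (5.4.3).

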5.4.2 Adverse Event Classification

Each AE will be assessed by the Investigator to determine if it is serious or non-serious³.

Serious Adverse Event

An SAE is an AE that

- Led to death
- Led to serious deterioration in the health of the Subject that either resulted in
 - A life threatening illness or injury, or
 - A permanent impairment of a body structure or body function, or
 - o Inpatient or prolonged hospitalization, or
 - Medical or surgical intervention to prevent life threatening illness or injury or permanent impairment to a body structure or a body function
- Led to fetal distress, fetal death or a congenital abnormality or birth defect.

Non-Serious Adverse Event

Any event that does not meet the definition of serious will be classified as non-serious.

5.4.3 Adverse Event Reporting and Coding

AEs will be reported on the appropriate CRF and documented in the Subject's permanent medical record. The Investigator at each Site is ultimately responsible for reporting AEs to the Sponsor and the IRB, when applicable. The Investigator shall supply the Sponsor and IRB with any additional requested information. AE reporting for a Subject begins once the Subject is enrolled in the study through study completion/withdrawal.

MD133254 Statistical Analysis Plan Template

The following information on each reported AE will be collected:

- AE Description
- AE Onset Date
- Primary Relationship
- Classification (Serious or Non-Serious)
- Action taken/Treatment required
- Outcome of Event
- Resolution Date

AEs will be coded using the Medical Dictionary for Regulatory Activities (MedDRA®).

5.4.4 Subject Death

Death is not an AE itself, but instead an outcome of an AE. Therefore, the cause of death, if known, should be the reported AE.

Any ongoing or unresolved AEs at the time of death will be indicated as ongoing/continuing on the CRF. Attempts should be made by the investigative Site to obtain death certificates, autopsy reports and device explants when at all possible.

5.5 Additional Analyses

5.5.1 Sensitivity Analysis of Endpoint Results

5.5.2 **Subgroup Analysis**

5.5.3 Imaging Analysis

All imaging data will be Site-reported. The Sites will provide review of imaging data collected during the study at pre-treatment and follow-up.

CONFIDENTIAL INFORMATION

MD133254 Statistical Analysis Plan Template

5.5.4 Mortality

For analysis of all-cause mortality over time (i.e. at 1-year), Kaplan Meier methodology will be used. Subjects without death reported before the end of the time period of interest will be censored at the Subject's last reported contact date or the end of the time period of interest, whichever date is earlier.

5.5.5 Reintervention

The definition of a reintervention is outlined in the study Protocol. A reintervention procedure will be determined as occurring using CEC adjudication from a specific question asked on the CEC CRF. Planned interventions (entered into the Planned Intervention CRF) will not count as reinterventions.

5.5.6 Device Events

5.5.7 Site Data Pooling

Site data will be pooled based on clinical comparability, i.e., the study Sites followed a common protocol, the study was monitored to assure compliance with the protocol and applicable government regulations, and the data collection and handling procedures were the same across study Sites.

6.0 Interim Analyses and Safety Monitoring Analyses (if applicable)

Safety data will be periodically reviewed by the DSMB. A comprehensive summary of reported adverse events will be reviewed by the DSMB.

Analysis of the study results will be ongoing throughout enrollment. Serial analyses of long-term results will occur during the follow up period

MD133254 Statistical Analysis Plan Template

7.0 Analysis Specifications

7.1 SAS Analysis Dataset Specifications

7.2 Statistical Output Specifications

7.3 Verification Level for Statistical Output

Levels of verification are defined in MD1113254 and will be as follows for all regulatory output:

- All Analysis Datasets Level I
- All Tables Level I
- All Listings Level II at a minimum

Doc Type: GC

8.0 Data Sets, Tables, Figures, and Listings

At a minimum, the following set of Tables, Figures, and Listings will be produced.

8.1 Analysis Tables

8.2 Analysis Listings

8.3 Analysis Figures

MD133254 Statistical Analysis Plan Template

